8.7.3 Analysis of Pharmacokinetic Variables

Not applicable.

8.7.4 Subgroup Analyses

Here the subgroups to be analysed are as follows:

1. de novo metastasis, recurrent metastasis and Overall

8.7.5 Exploratory Analyses

This is not applicable for this SAP. The same will be prepared by Rhizen and the analysis results will be shared for inclusion in the study report.

8.8 Analysis of Safety

8.8. 1 Duration of Treatment Exposure and Compliance to Study Treatment

Duration of Treatment

The duration of treatment (Treatment exposure) to the study medication for patient will be calculated as:

Treatment Exposure (day) = Last day of dosing – First Day of dosing + 1

A descriptive summary of duration of treatment (days) will be provided for each treatment group and by type of metastasis. In addition, a plot for duration on treatment will be provided per patient.

Measurements of Treatment Compliance

For each patient, the treatment compliance is captured for each cycle in the eCRF and is expressed as percentage. The treatment compliance, will be summarized descriptively per Cycle for each treatment group. This data will be listed for individual patient.

CONFIDENTIAL Page 18 of 106
Document Date: 12MAY2023. ST-AD-032 version 01

8.8.2 Adverse Events

Adverse events (AEs) will be coded using the Medical Dictionary for Regulatory Activities MedDRA Version 24.0 (Hierarchy) for the Safety Analysis Set.

The analyses of safety will be based on the frequency of adverse events and their severity for patients in each portion who received at least one dose of study treatment.

Adverse events will be summarised by system organ class and preferred term; a patient will only be counted once per system organ class and once per preferred term within a treatment according to the maximum NCI CTCAE v.5.0 grade attained. Patient counts and percentages and event counts will be presented for each treatment and overall for all the summaries.

Treatment Emergent Adverse Events (TEAEs) are events with start date on or after the date of first dose of treatment or events with start date prior to the date of first dose of treatment whose severity worsens on or after the date of first dose of treatment.

An overall summary of TEAEs (number and percentage of patients along with the number of events) will be presented with the following:

- Any non-TEAE
- Any TEAE
- Related TEAEs
- Serious TEAEs
- Related Serious TEAEs
- Grade >=3 TEAEs
- Related Grade >=3 TEAEs
- TEAEs leading to discontinuation
- Related TEAEs leading to discontinuation
- TEAEs leading to dose reduction
- Related TEAEs leading to dose reduction
- Serious TEAEs leading to discontinuation
- Related Serious TEAEs leading to discontinuation
- TEAEs leading to dose interruptions
- Related TEAEs leading to dose interruptions
- Fatal TEAEs
- Related Fatal TEAEs
- Protocol-Defined Adverse Events of Special Interest:
 - Pregnancy, abortion, birth defects/congenital anomalies
 - Overdose

Summaries showing the number of patients (n, %) along with number of events by SOC and PT will be provided for the following:

- 1. TEAEs
- 2. Grade 3. 4 and 5 TEAEs
- 3. Treatment-related TEAEs
- 4. TEAE with maximum CTCAE grade
- 5. Treatment-Emergent SAEs
- 6. Treatment-Related SAEs

Document Date: 12MAY2023

- 7. Treatment-related TEAEs with maximum CTCAE grade
- 8. TEAEs leading to dose reduction or interruptions
- 9. Treatment-related TEAEs leading to dose reduction or interruptions

Page 19 of 106 ST-AD-032 version 01

- 10. TEAEs leading to Discontinuation of Study Drug
- 11. Treatment-related TEAEs leading to Discontinuation of Study Drug
- 12. Deaths

No statistical inference between the treatments will be performed on adverse events.

The adverse events data will also be listed for individual patients.

- AEs
- Related TEAEs
- Treatment Emergent Grade 3, 4 and 5 AEs
- Treatment Related Grade 3, 4 and 5 AEs
- Treatment Emergent SAEs
- Treatment Related SAEs
- TEAE leading to discontinuation

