- 19. All visits will be done monthly from Cycle 3 onwards for 24 months (e.g. C4, C5, C6.... C26).
- 20. All visits for efficacy assessments will be done at 8-weekly intervals (± 7 days) for 24 months (e.g.C5, C7.... C26).
- 21. All patients will undergo the end-of-treatment (EOT) assessments within 7 days after last dose of study drug or discontinuation.
- 22. Patients must be followed telephonically for adverse events for 30 calendar days after the last dose of study drug.

CONFIDENTIAL Page 40 of 66

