2. INTRODUCTION

This statistical analysis plan (SAP) contains definition of analysis population(s), derived variables and statistical methods for efficacy and safety analysis.

The SAP is written based on the following documentation:

Document	Date	Version	
Protocol	29June2021	1.0	
eCRF	24Sep2021	1.0	
eCRF	16June2022	5.0	

Breast cancer is the most common cancer diagnosed in women and is the second leading cause of cancerrelated deaths. Based on these pre-clinical evidences with tenalisib and clinical evidences from other PI3K inhibitors, it is proposed that tenalisib has the potential to treat the patients with locally advanced and metastatic breast cancer.

The objective of the study is to assess the anti-tumour activity along with safety and efficacy of tenalisib at two different doses in order to identify the optimal dose that shows signal of clinical efficacy with an acceptable safety profile. This dose can be thus taken ahead for further development. Doses of 800 mg BID and 1200 mg BID are proposed in this Phase II study.

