5.1 Changes in the Conduct of the Study

The study was planned to administer tenalisib to all patients until disease progression or unacceptable toxicity for a maximum duration of 24 months. However this was changed and the study was closed earlier before all patients in the study showed disease progression. .

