Percentages are based on the total number of patients (N) in each treatment group.

Treatment-Emergent Adverse Events are those that start on or after the date of first dose of study drug.

Discontinuation refers to discontinuation of study drug.

Patients under the category 'Drug interruption followed by dose reduction' are counted in both the groups 'Drug interruption' and 'Dose reduction'.

^The dose reduction information is collated from the treatment exposure page of the eCRF.

n: Number of patients with any event, E: Number of events, TEAE: Treatment-Emergent Adverse Event.

Reference Listing 16.2.x.x

Document Date: 12MAY2023.

Protocol RP6530-2101

Page xx of yy

Table 14.3.1.2

Treatment-Emergent Adverse Events by System Organ Class and Preferred Term

Safety Analysis Set

System Organ Class Preferred Term		Tenalisib 800 mg (N=xx)	BID	,	Γenalisib 1200 mg (N=xx)	BID		Overall (N=xx)	
	Related n (%), E	Not Related n (%), E	Total n (%), E	Related n (%), E	Not Related n (%), E	Total n (%), E	Related n (%), E	Not Related n (%), E	Total n (%), E
At Least one TEAE	x (xx.x), xx	x (xx.x), xx							
SOC1 PT1 PT2 Etc.	x (xx.x), xx x (xx.x), xx x (xx.x), xx	x (xx.x), xx							

Percentages are based on the total number of patients (N) in each treatment group.

n: Number of patients with any event, E: Number of events, TEAE: Treatment-Emergent Adverse Event

A patient with two or more adverse events in the same system organ class (or with the same preferred term) is counted only once for that system organ class (or preferred term).

Treatment-Emergent Adverse Events are coded using MedDRA (version 24.0)

A patient experiencing an adverse event at multiple occasions with distinct relationships status with study treatment is counted under both "Related" and "Not Related" categories. The events (E) are counted as per their relationship with the study treatment.

System organ classes are sorted in alphabetical order. Preferred terms are sorted within system organ class by descending order of frequency of overall preferred terms.

Treatment-Emergent Adverse Events are those that start on or after the date of first dose of study drug.

Reference Listing 16.2.x.x

Program: xx.sas Table Generation: ddmmmyyyy hh:mm:ss

Use same format for

Table 14.3.1.3 Treatment-Emergent Grade 3, 4 and 5 Adverse Events by System Organ Class and Preferred Term – Safety Analysis Set

Protocol RP6530-2101 Page xx of yy

Table 14.3.1.4

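### AE incidence by dose is not adjusted for time at risk, so unequal time on treatment can distort the dose comparison in either direction

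*SAP*

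**What the plan says.** The purpose of comparing two doses, in the SAP Introduction, is to "identify the optimal dose that shows signal of clinical efficacy with an acceptable safety profile". Safety is one half of that choice.

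For adverse events, SAP section 8.8.2 says: "Patient counts and percentages and event counts will be presented for each treatment and overall for all the summaries". The footnote to the Table 14.3.1.1 shell fixes the denominator: "Percentages are based on the total number of patients (N) in each treatment group". The other AE shells follow the same layout of patients, percentage and number of events. Section 8.8.2 also says: "No statistical inference between the treatments will be performed on adverse events".

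On time at risk, SAP section 5.1 says: "The study was planned to administer tenalisib to all patients until disease progression or unacceptable toxicity for a maximum duration of 24 months". It then records that "the study was closed earlier before all patients in the study showed disease progression". Footnote 22 to the Schedule of Events (Protocol Table 5) sets the follow-up: "Patients must be followed telephonically for adverse events for 30 calendar days after the last dose of study drug".

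Exposure is reported, but apart from the AE tables. Section 8.8.1 says: "A descriptive summary of duration of treatment (days) will be provided for each treatment group and by type of metastasis". This feeds Table 14.3.6.1. No AE rate per unit of time, time to first AE, or AE incidence in a fixed window appears in the SAP text, the list of outputs or the shells.

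**The concern.** A patient's AE window runs from first dose to 30 days after the last dose. Its length is set by when the patient progresses, stops for toxicity or reaches study closure. If one dose keeps patients on drug longer, that arm has more time in which to record an event. Its percentage rises even when the rate of events per month is the same. Conversely, a dose with a higher event rate that patients leave sooner can show a similar percentage.

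Time on drug can differ for reasons other than efficacy. Protocol Table 8 allows Group 2 two dose reductions before discontinuation and Group 1 only one.

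At stake is the descriptive safety comparison used to choose the dose. No efficacy result is affected.

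**Working it through.** The documents give no AE rate, safety precision or exposure assumption by arm, so there is no stated figure to reproduce. The 13% precision in the sample-size section concerns the primary endpoint and does not bear on this point. What follows is an illustration.

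**Inputs from the documents.** 20 patients per arm; planning rate of 20% without progression at six months, used here as the share still on drug; 24-month maximum; 30 days of follow-up after last dose, a = 30/30.44 = 0.986 month.

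**Assumptions not in the documents.** Exponential time on drug; 40% in the other arm; the same constant AE hazard λ of 0.03 to 0.10 per month in both arms.

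**Time on drug.** μ = −ln(p6)/6.
- p6 = 0.20: μ = 1.609/6 = 0.268 per month; mean time on drug (1 − e^(−24μ))/μ = 3.7 months.
- p6 = 0.40: μ = 0.916/6 = 0.153 per month; mean 6.4 months.

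**Expected crude incidence.** P = 1 − e^(−λa) × [ μ/(μ+λ) × (1 − e^(−24(μ+λ))) + e^(−24(μ+λ)) ].

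For λ = 0.10:
- p6 = 0.20: 1 − 0.906 × 0.7285 = 0.340.
- p6 = 0.40: 1 − 0.906 × 0.6052 = 0.452.

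| λ per month | p6 = 20% | p6 = 40% | Gap (points) | Chance that the longer-exposed arm shows the higher % (20 per arm) |
|---|---|---|---|---|
| 0.03 | 12.7% | 18.7% | 6.0 | 0.62 |
| 0.05 | 19.8% | 28.1% | 8.3 | 0.67 |
| 0.10 | 34.0% | 45.2% | 11.2 | 0.71 |

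The last column comes from two independent binomials; the remainder is ties and reversals. In patients, the gap is 20 × 0.060 = 1.2 to 20 × 0.112 = 2.2.

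**Event counts are distorted too.** Expected events are 20 × λ × (mean time on drug + a). At λ = 0.10 this is 20 × 0.10 × 4.71 = 9.4 against 20 × 0.10 × 7.37 = 14.7.

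**A rate with the right denominator removes the gap.** Mean time to first event or end of follow-up is P/λ, so at λ = 0.10 it is 3.40 and 4.52 months per patient. Over 20 patients that is 6.8 first events in 68 patient-months and 9.0 in 90: 0.10 per month in both arms.

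**The direction is not fixed.** A hazard of 0.15 with p6 = 20% gives 44.7%; a hazard of 0.10 with p6 = 40% gives 45.2%. A 50% higher hazard disappears from the crude column.

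**Sensitivity.**
- 20% against 30%: gap 2.8 to 5.5 points over the same hazards.
- 20% against 20%: gap zero.
- Events possible only in the first two months, 20% against 40%, ignoring the 30-day follow-up: P = 1 − [ μ/(μ+λ) × (1 − e^(−2(μ+λ))) + e^(−2(μ+λ)) ]. At λ = 0.10 this is 14.2% against 15.7%, a gap of 1.5 points. Counting the 30 days of follow-up makes it smaller still.
- Early closure is not modelled, because its timing is not given. Cutting off long exposures would narrow the gaps.

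**The case against.** The strongest reply is that the SAP gives much more than crude AE percentages. By arm it reports treatment duration with mean, median and quartiles, numbers completing cycles 3, 6, 9, 12 and 15, maximum CTCAE grade, and AEs leading to reduction, interruption or discontinuation. Laboratory values, vital signs and ECGs are summarised by cycle. AE listings give onset day. A reader can divide event counts by total exposure. No inference between doses is made on AEs and no numerical safety rule selects the dose. Crude counts plus exposure are a conventional choice for a descriptive phase II study of this size.

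Most of this stands as context and limits the point. A reader might infer that safety is judged on crude percentages alone, or that the dose with longer treatment is bound to look more toxic. The documents support neither. Exposure and by-cycle data are reported. The planning rate is 20% for each group, so any difference between arms is an assumption. At 20 per arm one patient is 5 points, and the standard error of the difference in the illustration is 11 to 15 points. For AEs leading to discontinuation, the event itself ends dosing, so the simple story does not carry over.

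The core survives. A hand calculation from the tables gives at best a rough total-event rate. A first-event rate needs each patient's time to first event, which no table supplies. By-cycle laboratory summaries do not cover serious or Grade 3 or higher AEs. The lack of a test does not remove bias from columns that will be read side by side.

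**Conclusion.** The point holds in a limited form. AE incidence by dose is planned as patient counts, percentages of N and event counts, with no allowance for time at risk, in a study where time at risk depends on progression, tolerability and early closure. Unequal time on treatment can therefore distort the descriptive comparison either way.

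The 6 to 11 points are an expected gap under three assumptions: 20% against 40% on drug at six months, exponential time on drug, and an equal constant hazard of 0.03 to 0.10 per month. They do not predict what this trial will show.

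This is an inexpensive improvement worth making. It is not a contradiction in the plan.

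**What to change.** Change Table 14.3.1.1 only; leave the tables by system organ class and preferred term as they are. For Grade 3 or higher, serious and related TEAEs, and for TEAEs leading to dose reduction or to discontinuation, add by randomised arm:

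- patient-months at risk, from first dose to first event or to last dose + 30 days, whichever comes first;
- the exposure-adjusted first-event rate (patients with an event divided by patient-months at risk) with an exact Poisson confidence interval, labelled descriptive;
- incidence from first dose to C3D1 (study day 57) as a common early window. Note how many patients stopped before day 27, because their follow-up ends before day 57.

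Count only events with onset inside the same window. The TEAE definition in SAP section 8.8.2 has no end date, and Protocol section 7.1.3 still collects related events after 30 days. Without this cut, numerator and denominator would not match. List later related events separately.

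Keep the crude percentages and add no between-arm test. Add a footnote that person-time is by assigned arm and includes time after dose reduction, since under Protocol Table 8 a Group 2 patient may move to Group 1's starting dose.

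The cost is a few rows in one table, built from onset and dosing dates already held. The rate assumes a roughly constant hazard; the early window helps to check that.

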1.5.2 Rationale for Dose Selection

The safety and tolerability of tenalisib has been established up to doses of 1200 mg BID (total daily dose of 2400 mg) in patients with relapsed/refractory hematologic malignancies. No dose limiting toxicity was seen at this dose level. The efficacy of tenalisib at 800 mg BID has been evaluated as a single agent as well as in combination in patients with TCL and showed impressive response in this patient population. [19,20]

CONFIDENTIAL Page 22 of 66

In this study of breast cancer, the objective is to evaluate two doses of tenalisib and thus identify the optimal dose amongst the two which shows signal of clinical efficacy with an acceptable safety profile. This dose can be thus taken ahead for further development. Hence doses of 800 mg BID and 1200 mg BID are proposed in this Phase II study.

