7.6 Dose Modifications

In case of hematologic and non-hematologic toxicities, the dose modifications provided below (**Table 6** and **Table 7**) should be used as a guidance and should be determined as per PI's clinical judgement. The dose modifications are intended to be applied when the investigator determines the events related to tenalisib. If events (cytopenia) are deemed related to the underlying disease rather than tenalisib, dose reduction will be done as per the investigator's discretion. In case of drug withhold, tenalisib treatment can be resumed if:

- Patient recovers from grade 3-4 toxicity as defined in dose modification guidance below.
- No clinical or radiographic evidence of disease progression.
- Investigator believes the risk of progression outweighs the risk of further treatment.

If treatment is delayed >2 weeks, treatment continuation should be discussed with Medical monitor. The treatment should be permanently discontinued if withhold of study drug due to drug related toxicity is for > 28-days unless approved by medical monitor.

At the discretion of the investigator, a dose re-escalation may be permitted for patients who earlier has dose reduction. The decision should be taken after evaluating the emerging safety data and benefit and risk of re-escalation. Drug holidays are discouraged. Any patient in whom similar toxicity recurs at the reduced dose, it should be discussed with medical monitor to determine appropriate strategy on treatment continuation.

CONFIDENTIAL Page 46 of 66

Table 6: Dose modifications for hematologic toxicity

| CTCAE Grade | Action to be Taken |
|--|---|
| Hematologic toxicity | |
| Grade 3 Neutropenia $(1.0 \times 10^9/L < ANC \ge 0.5 \times 10^9/L)$ | Maintain dose level.Monitor ANC at least weekly. |

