| | Grade 3 Transaminitis (ALT/AST >5–20 x ULN; >5-20 x | | | |
| | baseline if baseline is abnormal): | | | |
| | Withhold tenalisib and monitor ALT/AST twice a weekly until | | | |
| | Grade ≤1; restart tenalisib at one dose lower*. | | | |
| | Initiate prednisone 1 mg/kg in case no improvement after | | | |
| | withholding tenalisib for 1 week. | | | |
| | • Monitor ALT/AST twice a weekly until Grade ≤1; restart | | | |
| | tenalisib at one dose lower* and taper steroid. | | | |
| | • If no immediate response to steroids within 7 days, initiate | | | |
| | mycophenolate mofetil. | | | |
| | • Discontinue if further dose modification required at lowest dose. | | | |
| | Grade 4 Transaminitis (ALT/AST >20 x ULN; >20x baseline if | | | |
| | baseline is abnormal): | | | |
| | Tenalisib should be permanently discontinued. | | | |
| | Bilirubin: | | | |
| | Grade 2 (> 1.5-3 x ULN; >1.5-3 x baseline if baseline is abnormal): | | | |
| | • Maintain tenalisib dose. Monitor at least weekly until ≤ 1x | | | |
| | ULN. | | | |
| | Grade 3 (> 3 -10 x ULN; > 3 -10 x baseline if baseline is abnormal): | | | |
| | • Withhold tenalisib. Monitor at least weekly until bilirubin is ≤ | | | |
| | 1x ULN. | | | |
| | • Restart tenalisib at one dose lower*. | | | |
| | Grade 4 (> 10 x ULN; >10 x baseline if baseline is abnormal): | | | |
| | Discontinue tenalisib permanently. | | | |
| Other non-hematologic to | xicities | | | |
| Grade 1 or 2 | None | | | |
| Grade 3 | Withhold tenalisib dose until toxicity Grade ≤2. Restart tenalisib at | | | |
| | one dose lower* if warranted. | | | |
| Recurrence of grade 3 | Withhold tenalisib dose until toxicity Grade ≤2; Restart tenalisib at | | | |
| toxicity | one dose lower* or discontinue treatment. | | | |
| Grade 4 | Withhold tenalisib dose until toxicity Grade ≤2; Restart tenalisib at | | | |
| | one dose lower* or discontinue tenalisib. | | | |
| Recurrence of grade 4 | Discontinue tenalisib | | | |

toxicity

*See 'Guidelines for dose reduction' below.

Note: The drug interruption and dose modification should be discussed with medical monitor.

Page 49 of 66 CONFIDENTIAL

| Table 6. Guidance on Tenansio Dose reduction | | | | | | |
|--|--------------------|--------------------------------|--------------------------------|--|--|--|
| Group | 1st Dose reduction | 2 nd Dose reduction | 3 rd Dose reduction | | | |
| Group 1 (Tenalisib 800 mg BID) | 400 mg BID | Discontinue | - | | | |

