| Group 2 (Tenalisib 1200 mg BID) | 800 mg BID | 400 mg BID | Discontinue | | | |

Table 8: Guidance on Tenalisib Dose reduction

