Patients Disposition

All Patients

Page xx of yy

	Tenalisib 800 mg BID	Tenalisib 1200 mg BID	Overall	
Drug interruptions due to AEs	xx (xx.x)	xx (xx.x)	xx (xx.x)	
Drug discontinuation due to AEs	xx (xx.x)	xx (xx.x)	xx (xx.x)	
Dose reduction due to AEs ^	xx (xx.x)	xx (xx.x)	xx (xx.x)	

[#] Number of patients discontinued at the end of the study.

Percentages are based on the total number of patients randomized in each treatment group.

Percentages for reason of discontinuation are based on the total number of patients discontinued in each treatment group.

Safety Analysis Set includes all patients who received at least one dose of study medication.

Intent-to-Treat Analysis Set includes all patients who received at least one dose of study medication.

Per Protocol Analysis Set includes all patients in the Intent-to-Treat Set without major protocol deviations.

Patients under the category 'Drug interruption followed by dose reduction' are counted in both the groups 'Drug interruption' and 'Dose reduction'.

^The dose reduction information is collated from the treatment exposure page of the eCRF.

AE:Adverse Event

Reference Listing xxxxxx

Document Date: 12MAY2023

Program: xx.sas Table Generation: ddmmmyyyy hh:mm:ss

^{*}A patient may have multiple reasons for discontinuation from the study and such patients are counted in each reason for discontinuation as reported in the eCRF.

^{\$}A patient who had a non-related adverse event which was documented as "death due to unknown cause" is also recorded an adverse event leading to study discontinuation.

Protocol RP6530-2101
Table 14.1.2.1
Summary of Protocol Deviations
Safety Analysis Set

Page xx of yy

	Tenalisib 800 mg BID	Tenalisib 1200 mg BID	Overall
	(N=XX)	(N=XX)	(N=XX)
	n (%), E	n (%), E	n (%), E
All Protocol Deviations	xx (xx.x), xx	xx (xx.x), xx	xx (xx.x), xx
Major Protocol Deviations	xx (xx.x), xx	xx (xx.x), xx	xx (xx.x), xx
Minor Protocol Deviations	xx (xx.x), xx	xx (xx.x), xx	xx (xx.x), xx
Patients with at least one protocol deviation	xx (xx.x), xx	xx (xx.x), xx	xx (xx.x), xx
Study medication therapy	xx (xx.x), xx	xx (xx.x), xx	xx (xx.x), xx
Study Procedure out of time frame/Missing	xx (xx.x), xx	xx (xx.x), xx	xx (xx.x), xx
Lab Procedure/Assessment missing	xx (xx.x), xx	xx (xx.x), xx	xx (xx.x), xx
Visit Schedule / Out-of-Window	xx (xx.x), xx	xx (xx.x), xx	xx (xx.x), xx
Concomitant Medications	xx (xx.x), xx	xx (xx.x), xx	xx (xx.x), xx
Consent Procedure	xx (xx.x), xx	xx (xx.x), xx	xx (xx.x), xx

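### The counts of adverse events leading to discontinuation are not like-for-like between the two doses, because the 1200 mg arm has one more reduction step before stopping

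*SAP*

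**What the plan says.** Protocol 7.6, Table 8, sets the reduction steps by arm. For the lower dose it reads "Group 1 (Tenalisib 800 mg BID) | 400 mg BID | Discontinue"; for the higher dose, "Group 2 (Tenalisib 1200 mg BID) | 800 mg BID | 400 mg BID | Discontinue". Tables 6 and 7 tie some stops to the bottom of that ladder, for example after recurrent Grade 4 neutropenia or Grade 3 transaminitis: "Discontinue if further dose modification required at lowest dose". Other stops bypass the ladder in both arms. For Grade 4 transaminitis Table 7 says "Tenalisib should be permanently discontinued". Severe pneumonitis, life-threatening rash or diarrhoea, Grade 4 bilirubin, recurrent Grade 4 toxicity and toxicity holds beyond 28 days are also stopping events. Section 7.6 adds that the modification tables "should be used as a guidance and should be determined as per PI's clinical judgement".

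SAP 8.8.2 reports TEAEs leading to discontinuation, to dose reduction and to interruption as separate rows by arm, each for all and for related events, for example "Related TEAEs leading to discontinuation". The shells are Table 14.3.1.1 (overall summary) and Tables 14.3.1.9 to 14.3.1.12. The disposition shell, Table 14.1.1.1, has its own row, "Drug discontinuation due to AEs". A footnote to Table 14.3.1.1 makes clear that discontinuation means stopping study drug, not leaving the assigned dose. Protocol 1.5.2 gives the purpose of the trial: to "identify the optimal dose amongst the two which shows signal of clinical efficacy with an acceptable safety profile".

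**The concern.** What turns a toxicity history into a discontinuation depends on the arm. A patient who needs two step-downs is a discontinuation in Group 1, and in Group 2 a patient with two reductions who is still on drug. Nothing in the SAP or its shells tells the reader this.

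The rows beside it do not fully repair it. A patient who is reduced and later stops appears in both the reduction and the discontinuation row, so the two cannot be added. The reduction row omits patients who stop directly from the assigned dose. Tables 14.3.1.9 and 14.3.1.10 combine reduction with interruption, never with discontinuation. So no planned table shows how many patients could not stay on their assigned dose because of toxicity.

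The trial exists to choose between two doses and states no selection rule. The choice will be made by reading descriptive tables, and toxicity discontinuation is a figure readers naturally turn to. If it flatters the higher dose, the tolerability cost of 1200 mg may be underestimated.

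**Working it through.** The documents state no discontinuation or step-down rate, so there is no planned figure to reproduce. The check asks what Table 8 implies under assumed rates.

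**Inputs from the documents:** 20 patients per group (Protocol 3.2); Group 1 stops at its second step and Group 2 at its third (Table 8).

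**Assumptions:** s is the probability that a patient at a given dose has a toxicity needing a step down. h is the probability of a direct stop at that dose, outside the ladder. Progression before the ladder is used up is ignored.

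**Formulas:**
- Group 1: P1 = h800 + s800 × (h400 + s400)
- Group 2: P2 = h1200 + s1200 × P1

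**Step 1: ladder stops only (all h = 0), independent steps.** Then P1 = s800 × s400 and P2 = s1200 × P1.

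| s1200 / s800 / s400 | Group 1 | Group 2 | Expected of 20 |
|---|---|---|---|
| 0.2 / 0.15 / 0.15 | 2.25% | 0.45% | 0.45 v 0.09 |
| 0.3 / 0.3 / 0.3 | 9.0% | 2.7% | 1.80 v 0.54 |
| 0.5 / 0.3 / 0.2 | 6.0% | 3.0% | 1.20 v 0.60 |
| 0.5 / 0.4 / 0.3 | 12.0% | 6.0% | 2.40 v 1.20 |
| 0.8 / 0.3 / 0.2 | 6.0% | 4.8% | 1.20 v 0.96 |
| 1.0 / 0.3 / 0.2 | 6.0% | 6.0% | 1.20 v 1.20 |

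Group 2 is never higher, and the arms are equal when s1200 = 1. The gap runs from 0 to about 1.3 patients and is below one in four of the six rows. In the third row 30% and 50% leave the assigned dose (s800 v s1200), the opposite order from 6% and 3%.

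**Step 2: correlation within patients.** Patients who react at one dose may react at the next. With s = 0.5/0.3/0.2 and a simulated normal frailty, the rates for Group 1 v Group 2 are 9.2% v 6.8% at correlation 0.3, 12.9% v 11.7% at 0.6 and 20.0% v 20.0% at 1.

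**Step 3: direct stops added,** s = 0.5/0.3/0.2, independent steps.
- h = 0.05 at every dose: P1 = 0.05 + 0.3 × 0.25 = 12.5%; P2 = 0.05 + 0.5 × 0.125 = 11.3%. Group 2 is slightly lower.
- h = 0.10/0.05/0.02: P1 = 0.05 + 0.3 × 0.22 = 11.6%; P2 = 0.10 + 0.5 × 0.116 = 15.8%. Group 2 is higher. Leaving the assigned dose (h + s) is 35% v 60%. The ratio between arms is 60/35 = 1.7 on that measure and 15.8/11.6 = 1.4 on the discontinuation row, so the order is right but the difference is compressed.

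The arms tie when h1200 = (1 − s1200) × P1. With P1 = 11.6% this is 8.1%, 5.8% and 3.5% for s1200 = 0.3, 0.5 and 0.7. Above these values 1200 mg shows more discontinuations despite the longer ladder. Over random draws with s up to 0.6 and h up to 0.2, both ordered so that higher doses are more toxic, Group 2 came out lower in 7.8%. That share depends on the ranges drawn, but it shows that outright reversal needs few direct stops.

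**Step 4: visibility at 20 per arm.** With true rates of 6% v 3%, the observed Group 1 count exceeds Group 2 with probability 51%, ties with 31% and is lower with 18%.

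**The case against.** The case against is substantial.

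- A reader might infer from Table 8 that the discontinuation count must be lower at 1200 mg however toxic that dose is. The documents do not support this. The row counts every TEAE discontinuation, many stopping rules bypass the ladder in both arms, and Step 3 shows that direct stops can put 1200 mg higher. Even for ladder stops the arms become equal when s1200 = 1 or within-patient correlation is complete.
- A reader might also take the overall shortfall to be the ladder share of all stops times (1 − s1200). That requires equal direct stops in both arms, which conflicts with supposing 1200 mg to be more toxic.
- The display is descriptive. SAP 8.8.2 rules out inference between arms on adverse events, Protocol 9.4.2 does not list discontinuation among the safety endpoints, and no decision rule uses this row.
- Stopping the drug is a fact about each regimen with its own reduction scheme, not a misclassification. The ladder is guidance under investigator judgement, and re-escalation is allowed.
- Reductions, interruptions, Grade 3 or higher, serious and fatal TEAEs stand in the same summary. It gives event counts as well as patients, so repeat reductions can show. Listings 16.2.1.4, 16.2.5.1 and 16.2.5.2 carry the individual detail.
- The larger assumed rates may be too high. Protocol 1.4 reports related Grade 3 or higher ALT and AST increases of 7.4% each and neutropenia of 4.4%, and 1.5.2 reports no dose-limiting toxicity at 1200 mg.

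All of this stands, and it limits the point to interpretation. It does not make the row comparable. A descriptive count can mislead without a p-value, event counts do not separate first from second steps, and a reader should not have to rebuild the comparison from listings.

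**Conclusion.** The discontinuation rows are not like-for-like, because Group 2 has one more reduction step than Group 1. For the same toxicity, ladder stops tend to be fewer at 1200 mg. The row can therefore understate the tolerability difference or, where direct stops are few and within-patient correlation is weak, reverse it. The direction is not fixed, and the reduction and interruption rows give partial protection.

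The size is illustrative only, since it rests on assumed rates. At 20 per arm it is about one patient or less in most scenarios, and chance alone could hide it or turn it round. This is a cheap improvement to the safety tables, not a flaw that invalidates them.

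**What to change.** Leave Table 8 unchanged. In SAP 8.8.2 and in Tables 14.3.1.1 and 14.1.1.1, add by arm, for all and for related events:

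1. Patients with any TEAE leading to the first reduction or the discontinuation of the assigned dose, named as the like-for-like tolerability summary between doses.
2. The discontinuation row split into stops from the assigned dose and stops from a reduced dose.
3. A footnote that total discontinuations are to be read with the reduction rows, because the arms have different numbers of reduction steps.

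A row for second step-downs is not needed. If one is wanted, restrict it in both arms to patients who already had a first reduction. Otherwise Group 2 could take in direct stops from 1200 mg with no counterpart in Group 1.

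The cost is SAP wording and a few table rows. The dose-reduction, action-taken and last-dose data are already in the planned listings, so no protocol amendment, new data or additional patients are needed. The downside is slightly longer tables and a summary that may look less favourable for 1200 mg.
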